6.1.2 Categorical variables at follow-up and all other numerical variables

For categorical variables, the procedure explained above cannot be performed; as such, for these variables, a listing of the treatment start date (or the closest date) and the date of the follow-ups recorded will be sent for subsequent assignment to the corresponding month. This would also apply to all other numerical variables not covered in the previous section (e.g. BMI, albumin, etc.), as there will be no weighted increase for these variables over the visits.

7 DATABASE LOCK AGREEMENT

If abnormal and/or inconsistent values are detected in any result table, the database will not be reopened for modification; however, the abnormal data will be highlighted, as well as its processing method (e.g. through assignment of non-existent data or deletion of the case depending on the statistical method to be used in the analysis in question).

Any modification to this table will be reflected in the report in writing, as well as the procedure followed (e.g. assignment of non-existent data, interpolation, case deletion, etc.).

For the final statistical analysis, the database will only be reopened and the study data and tables that could consequently be modified will be re-analyzed if the reconsideration of the initial analysis is evaluated jointly with the sponsor.

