4 STUDY POPULATION

The current study population consists of ATTRv and ATTRwt patients who have participated in studies B3461028 and B3461045 in Spain, with cardiac and neurologic involvement receiving or who have received Tafamidis free acid 61 mg for at least 12 months, and who are in neurological follow-up for no less than 12 months. According to the protocol, patients who meet the inclusion criteria are estimated to be: 10 with ATTRv and 10 with ATTRwt.

Individuals participating in the TRAMA study must meet all of the inclusion and none of the exclusion criteria.

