6 METHODS FOR THE STATISTICAL ANALYSIS

The analysis methods to be used to achieve the study objectives and draw up the descriptive content for the variables are detailed below.

❖ UNIVARIATE ANALYSIS

Quantitative variables will be described with centralization and scattering measures (mean, SD (standard deviation), median, minimum, maximum, Q1 (first quartile), Q3 (third quartile and N).

Qualitative variables will be described by absolute and relative frequencies. Two columns of percentages will be presented: Total Percentage (Total %) and Valid Percentage (Valid %):

- Total Percentage (%): Percentage of the sum of valid responses plus missing values, i.e. of the total of the sample under study.
- Valid percentage (Valid %): Percentage of total valid responses, i.e. with data on the variable.

In subgroup analyses, only the valid % with respect to the total for each group will be presented.

For questions with more than one answer option, **multiple response** tables will be shown. Two percentage column will be shown in these tables:

- Total percentage (%) Percentage of the sum of valid responses plus missing values, i.e. of the total of the sample under study. Since it is multiple choice, the sum of percentages does not have to be 100 (the percentage may be exceeded).
- Valid percentage (%) Percentage of the number of patients with at least one given answer from among the possible answers. Since it is multiple choice, the sum of percentages does not have to be 100 (the percentage may be exceeded).

Missing data will not be attributed and will be left as lost data.

Statistical analysis of variables collected in the study will be performed using the SPSS statistical program.

NOTE 1: Due to the small number of patients available in the study, no comparisons will be made and the associated p-value will not be shown. Only descriptive analyses will be presented.

NOTE 2: The texts collected in open fields will not be grouped, other than to standardize format and spelling. If desired, any grouping must be performed by the sponsor and as an additional table to the description of what is included in the database.

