6.1 Visit reassignment

6.1.1 Numerical variables at follow-up (neurological and scales)

In the section on variables in follow-up, there are visit dates and no months assigned to those visits. To avoid time variability and ensure consistency of the data, for each quantitative follow-up variable, the following procedure will be calculated. All values will be assigned, as of the follow-up date, weighing the assignments based on the recorded follow-ups.

1. Months between visits:

Firstly, the date difference between the first follow-up and the start time will be calculated for the variable in question. Values will be assigned to those visits that are close to this difference or lower, i.e. if the difference is 25 months, visits up to Month 24 will be allocated (see note 3 below).

2. Monthly unit change (exchange rate):

$$\frac{(\text{value at follow-up visit} - \text{value at start of treatment visit})}{\text{months between visits}}$$

3. Increment for each visit:

Monthly unit change x 6

Monthly unit change x 12

Monthly unit change x 18

Monthly unit change x 24

Monthly unit change x 36

4. Value assigned at each visit:

Baseline value + Increment for each visit

NOTE 3:

- In case only one follow-up is available and the total follow-ups cannot be assigned, the “last value carried forward” (LVCF) method will be used, so the last value obtained will be carried over to the end.
- If more than one follow-up is available and the difference between their dates is:
 - Less than 5 months, the value will not be allocated, as the two visits would be very close to each other.
 - Greater than 5 months and less than 10 months, the value of that follow-up will be assigned to the next follow-up pending assignment. That is, if the assignment of the first follow-up

reaches month 24, the assignment of month 36 would be considered as the value recorded in the second follow-up.

– Otherwise, if the difference is greater than 10 months, the values will be assigned with the algorithm from step 1 taking the previous follow-up as baseline.

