12 ANALYSIS OF THE OBJECTIVES

12.1 Primary objective

“To determine the efficacy of Tafamidis free acid 61 mg in ATTRv patients with neurologic involvement included in studies B3461045 and/or LTE (B3461045) in Spain through changes in the 12-month NIS scale”

Primary variable: Neuropathy Impairment Score (NIS).

NOTE: ATTRv patients are considered to be those who have indicated “Mutation” in the genotype (Data related to the disease at diagnosis).

See resolution of this objective in 10.3.1 (month 12).

Additionally, the results will be presented for the percentage of patients responding to treatment of the change at month 12 with respect to the initial value. The N and % of patients responding to treatment will be calculated, defining responder as:

- change at 12 months compared to the initial data <4p in NIS, patients who have obtained less than 4 points in the NIS in month 12

Patients who do not meet the previous condition will be considered non-responders. If complete data is not available, the value will be left as missing.

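### SAP 7 lets values or cases be changed after the result tables are seen, with no criterion and no requirement to show the unmodified result

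*SAP*

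**What the plan says.** SAP 7 (Database lock agreement) has three parts.

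- **Trigger.** "If abnormal and/or inconsistent values are detected in any result table, the database will not be reopened for modification". The data concerned are instead highlighted together with how they were processed, for example "through assignment of non-existent data or deletion of the case depending on the statistical method to be used in the analysis in question".
- **Reporting.** "Any modification to this table will be reflected in the report in writing, as well as the procedure followed". The examples of procedure given here add interpolation.
- **Reopening.** For the final analysis the database may be reopened, and the affected tables rerun, only "if the reconsideration of the initial analysis is evaluated jointly with the sponsor".

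Elsewhere, SAP 6 states: "Missing data will not be attributed and will be left as lost data". SAP 12.1 repeats this for the month-12 responder result: "If complete data is not available, the value will be left as missing". SAP 6.1.1 sets out a visit-reassignment algorithm in advance, including a carry-forward step ("so the last value obtained will be carried over to the end"). SAP 9.7 and 10.2 set out in advance that recalculated BMI and mBMI override the recorded figures.

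On numbers, SAP 4 says that "patients who meet the inclusion criteria are estimated to be: 10 with ATTRv and 10 with ATTRwt".

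**The concern.** The trigger lies in the result tables, so the decision is taken with outcomes in view. SAP 7 gives no definition of abnormal or inconsistent, no decision-maker, and no rule for which action applies to which variable. It asks for a report of what was changed, but not for the result without the change. Its scope is any result table, which includes the month-12 NIS table that answers the primary objective.

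Two separate faults follow. Putting an interpolated value in place of a recorded one sits badly with the rule that gaps are left as gaps. Deleting a case is an exclusion chosen after the results, which SAP 6 does not address at all. Reopening the database after the initial analysis is a further route to the same end, also without a criterion.

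The study has one treated group and a primary subgroup of about 10, so one patient is a tenth of the evidence on the primary objective.

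**Working it through.** **Inputs.** n = 10 ATTRv patients (SAP 4; an estimate of available patients, not a calculated sample size). Responder: NIS change below 4 points at month 12 (SAP 12.1). In subgroup tables only the valid percentage is shown (SAP 6). The documents give no SD for NIS change and no sample-size or power figure to reproduce, so the distances and patient values below are assumptions.

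**Responder share.** With k responders out of 10:

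| Action on one patient | Formula | k = 5 | k = 7 | k = 9 |
|---|---|---|---|---|
| None | k/10 | 50.0% | 70.0% | 90.0% |
| Non-responder deleted | k/9 | 55.6% | 77.8% | 100% |
| Non-responder's value replaced so that it counts as a response | (k+1)/10 | 60.0% | 80.0% | 100% |
| Responder deleted | (k−1)/9 | 44.4% | 66.7% | 88.9% |

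Setting a value to missing has the same effect as deletion here, because the ATTRv table shows only the valid percentage.

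**Mean change.** Deleting a patient who lies d points from the group mean moves the mean by d/(n−1) = d/9. For d = 10, 20 and 30 the shift is 1.1, 2.2 and 3.3 NIS points, against a responder threshold of 4.

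**Direction.** Two constructed examples:

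- Nine patients at +2 and one at +20: mean (9×2 + 20)/10 = 3.8, responders 9/10. After deletion the mean is 2.0 and responders are 9/9. The result looks better.
- Nine patients at +2 and one at −20: mean (9×2 − 20)/10 = −0.2, responders 10/10. After deletion the mean is 2.0 and responders are 9/9. The mean looks worse.

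The median is +2 before and after deletion in both examples.

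**Worst case for the tests.** SAP 10.3.1 plans paired tests where possible but states no significance level. Assume a two-sided 5% level, normal differences and no true effect, and suppose the single least favourable patient is always deleted. In 200,000 simulated runs, the chance of a falsely favourable result at n = 10 rises from 2.5% to about 8.7% (to 8.9% at n = 8 and 7.5% at n = 20). This marks how bad one deletion could be; nothing in the documents says that it would be used this way.

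**The case against.** The strongest reply is that this is a residual data-error clause with safeguards. The first sentence of SAP 7 keeps the database closed, abnormal data are highlighted, and every modification is reported in writing. SAP 10.3.1 plans a per-patient NIS listing from start of treatment to month 36. Protocol 9.8 requires queries for all patients to be resolved before the database closes.

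These points stand and lower the stakes, but they do not close the gap. SAP 7 does not require the unmodified estimate. The listing covers NIS only, and the SAP does not say whether it shows original or modified values. The queries in Protocol 9.8 are described as aimed at important missing variables, so they may not catch implausible recorded ones.

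A reader might also infer three stronger things that the documents do not support.

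- **That the SAP authorises invented values.** The SAP reads as a translation: its change log calls the plan a PAE, and SAP 6 writes of attributed and lost data. Assigning non-existent data may simply mean coding the value as missing. Interpolation and case deletion are named separately, so the point does not depend on this phrase.
- **That SAP 6 says the opposite of SAP 7.** SAP 6 governs missing data, whereas SAP 7 also covers recorded values that look wrong. The misfit is with interpolating a replacement. Case deletion is a different fault.
- **That the result will be tilted towards tafamidis.** In a progressive disease a large worsening could look abnormal, but so could an implausible improvement. SAP 7 does not say that a plausible worsening counts as abnormal, and the SAP also reports medians and quartiles, which move less.

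**Conclusion.** The point holds in limited form. SAP 7 permits case deletion, interpolation, a third action of unclear meaning, and reopening of the database, all after result tables have been seen, with no criterion and no obligation to show the result without the change. With about 10 ATTRv patients, one such decision moves the responder share by up to 10 percentage points (for example 70% to 77.8% by deletion or 80% by replacement). It moves the mean NIS change by a ninth of that patient's distance from the mean. The direction cannot be stated in advance.

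The sizes rest on the SAP's estimate of 10 patients and on one patient being affected; the NIS distances and patient values are illustrative. SAP 7 covers all tables, so about 20 patients fall under it in total. The carry-forward and interpolation in SAP 6.1.1 also sit awkwardly with the no-imputation rule, but they are fixed in advance and are not the fault described here. This is a cheap improvement to the plan; it does not show that any result is wrong.

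**What to change.** Reword SAP 7 as follows.

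1. The main analysis uses the locked data, with only the derivations already prespecified in SAP 6.1 (visit reassignment, including carry-forward) and in SAP 9.7 and 10.2 (BMI and mBMI recalculation).
2. Scores outside the ranges the SAP states (NIS 0 to 244, NIS-LL 0 to 88, Norfolk QoL-DN −4 to 138, FAP-RODS 0 to 68, COMPASS-31 0 to 100) and impossible dates are set to missing, by a rule fixed before any table is produced.
3. After tables are seen, no other value is replaced and no patient is removed in the main result. This includes variables for which the SAP states no range, such as nerve amplitudes, Sudoscan, renal values and intraocular pressure.
4. Any other change, including one made after reopening the database jointly with the sponsor, is reported as a labelled sensitivity result beside the unmodified result.

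The cost is SAP wording and a few extra table rows; no new data are needed. The downside is that a true error inside the valid range stays in the main result. It would be footnoted, with the corrected result shown beside it.

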8 DESCRIPTIVE STATISTICAL ANALYSIS (STUDY INCLUSION)

Analyses will be performed on the total population and subgroup based on genotype (ATTRv and ATTRwt). Descriptive analyses will be presented with no comparisons between genotype groups.

8.1 Treatment-related variables

Frequencies (N. %) will be shown for the following qualitative variables:

- Has the patient participated in study B3461028? (Yes / No)
- Has the patient participated in study B3461045? (Yes / No)
- Patients who participated in the above two studies.

8.1.1 ATTR Treatment Start Date

Frequencies (N. %) will be shown for the following qualitative variables:

- Commercial medication (Tafamidis 20 mg) (Yes / No)
- Treatment regimen in ATTR-ACT (B3461028) or LTE (B341045) trial of origin (multiple choice table):
 - ATTR-ACT or LTE Tafamidis 20 mg
 - ATTR-ACT or LTE Tafamidis 80 mg
 - ATTR-ACT or LTE Tafamidis 61 mg
- Is the patient currently on Tafamidis free acid 61 mg? (Yes / No)

Descriptive statistics (Mean, SD, Median, Minimum, Maximum, Q1, Q3 and N) of the following quantitative variables will be displayed:

- Duration for the following treatments (in months):
 - ATTR-ACT or LTE Tafamidis 20 mg, calculated as end date - start date.
 - ATTR-ACT or LTE Tafamidis 80 mg, calculated as end date - start date.
 - ATTR-ACT or LTE Tafamidis 61 mg, calculated as end date - start date. If still on treatment, up to the enrollment date will be considered (enrollment date - start date).

8.2 Demographic variables

8.2.1 Demographic data

Descriptive statistics (Mean, SD, Median, Minimum, Maximum, Q1, Q3 and N) of the following quantitative variable will be shown:

- Age at enrollment (years)

Frequencies (N. %) will be shown for the following qualitative variable:

- Sex (Male / Female)

8.2.2 Disease-related data at diagnosis

Descriptive statistics (Mean, SD, Median, Minimum, Maximum, Q1, Q3 and N) of the following quantitative variables will be displayed:

- Age at onset of the disease (years)
- Age at diagnosis (years)

Frequencies (N. %) will be shown for the following qualitative variables:

- Genotype (Mutation / Wildtype):
 - Mutations (Val142Ile / Ile88Leu / Thr80Ala / Val50Met / Pro44Ser / Other) (multiple choice chart). The other specifications listed will be shown.
 - For each mutation (Homozygosity / Heterozygosity / Compound heterozygosity).

8.2.3 First disease-related sign or symptom

Frequencies (N. %) will be shown for the following qualitative variables:

- Gastrointestinal disorders (Yes / No). If yes, a multiple choice table will be shown for:
 - Diarrhea
 - Frequency (< 2/week | 2/week | ≥ 3/week)
 - Nausea/vomiting
 - Severe constipation
 - Unintentional weight loss
 - Alternating episodes of diarrhea and constipation
 - Early satiety

- Urological disturbances (Yes / No). If yes, a multiple choice table will be shown for:
 - Urinary tract infections
 - Urinary retention
 - Urinary incontinence
 - Type (stress / permanent)
- Ophthalmological disturbances (Yes / No). If yes, a multiple choice table will be shown for:
 - Vitreous opacities
 - Glaucoma
 - Conjunctival vessel changes
 - Pupillary changes
- CNS changes (Yes / No). If yes, a multiple choice table will be shown for:
 - Seizures
 - Transient ischemic attack or stroke
 - Cognitive impairment
- Autonomic neuropathy changes (Yes / No). If yes, a multiple choice table will be shown for:
 - Sweating disturbance
 - Sexual dysfunction
 - Grade (Mild / Moderate)
 - Orthostatic hypotension
 - Type (Absent / Dizziness / Syncope)
- Peripheral neuropathy abnormalities (Yes / No). If yes, a multiple choice table will be shown for:
 - Allodynia/pain
 - Loss of sensitivity to temperature
 - Paresthesia / numbness / sensory loss
- Heart disorders (Yes / No). If yes, a multiple choice table will be shown for:
 - Conduction block
 - Cardiomyopathy

- Arrhythmia
- Other. The other specifications collected in cardiac abnormalities will be shown.
- Other. The other specifications listed will be shown.

9 CLINICAL PARAMETERS

Clinical parameters available in the medical history in the 12 months before inclusion in studies B3461028 and/or LTE B3461045, or inclusion in studies B3461028 and/or LTE B3461045 (start of treatment with Tafamidis 61 mg). Each section will indicate the most recent of the two time points.

Analyses will be performed on the total population and subgroup based on genotype (ATTRv and ATTRwt). Descriptive analyses will be presented with no comparisons between genotype groups.

9.1 Neurological variables

9.1.1 *NIS (Neuropathy Impairment Score)*

Descriptive statistics (Mean, SD, Median, Minimum, Maximum, Q1, Q3 and N) of the following quantitative variable will be shown:

- NIS result (total score ranges from 0 to 244)

9.1.2 *NIS-LL (Neuropathy Impairment Score Lower-Limbs)*

Descriptive statistics (Mean, SD, Median, Minimum, Maximum, Q1, Q3 and N) of the following quantitative variable will be shown:

- NIS-LL result (total score ranges from 0 to 88)

9.1.3 *FAP (Familiar Amyloidotic Polyneuropathy stage)*

Frequencies (N. %) will be shown for the following qualitative variable:

- FAP result (Asymptomatic / Free ambulation or stage 1 / Supportive ambulation or stage 2 / Wheelchair-bound or bedridden or stage 3)

9.1.4 *PND (Polyneuropathy Disability Score)*

Frequencies (N. %) will be shown for the following qualitative variable:

- PND result (Asymptomatic / I Sensory disturbances, normal gait / II Sensory disturbances, altered gait not requiring support / IIIA Gait requiring support / IIIB Gait requiring two supports / IV Wheelchair or bedside)

9.2 **Neurophysiological variables**

Frequencies (N. %) will be shown for the following qualitative variables:

- Nerve conduction study (EMG)
 - Axonal / Demyelinating (Altered / Unaltered)
- Sudoscan Electrocuteaneous Conductance (ECC):
- RR Interval Variability (Altered / Unaltered)

Descriptive statistics (Mean, SD, Median, Minimum, Maximum, Q1, Q3 and N) of the following quantitative variables will be displayed:

- Nerve conduction study (EMG)
 - Ulnar / peroneal CMAP amplitude (mV)
 - Ulnar / Sural SNAP amplitude (μ V)
- Sudoscan Electrocuteaneous Conductance (ECC):
 - Hands result (μ S)
 - Feet result (μ S)

9.3 Scales

9.3.1 *Norfolk QoL-DN (Norfolk Quality of Life-Diabetic Neuropathy)*

Descriptive statistics (Mean, SD, Median, Minimum, Maximum, Q1, Q3 and N) of the following quantitative variable will be shown:

- Norfolk QoL-DN result (range -4 to 138)

9.3.2 *FAP-RODS (Familial Amyloid Polyneuropathy Specific Rasch-Built Overall Disability Scale)*

Descriptive statistics (Mean, SD, Median, Minimum, Maximum, Q1, Q3 and N) of the following quantitative variable will be shown:

- FAP-RODS result (total score ranges from 0 to 68) (0=Lesser ability to perform daily activities and 68=Greater ability to perform daily activities)

9.3.3 *Composite Autonomic Symptom Score 31 (COMPASS-31) autonomic symptoms questionnaire*

Descriptive statistics (Mean, SD, Median, Minimum, Maximum, Q1, Q3 and N) of the following quantitative variable will be shown:

- COMPASS-31 result (total score ranges from 0 to 100) (0=Lesser severity of dysautonomia and 100=Greater severity of dysautonomia):

9.4 Renal Assessment Variables

Frequencies (N. %) will be shown for the following qualitative variables:

- Proteinuria (Yes / No)
- Albumin/Microalbuminuria (Yes / No)

Descriptive statistics (Mean, SD, Median, Minimum, Maximum, Q1, Q3 and N) of the following quantitative variables will be displayed:

- Proteinuria result (g/24h)
- Albumin / microalbuminuria result (mg/g)
- Estimated glomerular filtration rate (eGFR) (mL/min/1.73m²)

9.5 Ophthalmologic Assessment Variables

Descriptive statistics (Mean, SD, Median, Minimum, Maximum, Q1, Q3 and N) of the following quantitative variable will be shown:

- Intraocular Pressure result (mmHg)

Frequencies (N. %) will be shown for the following qualitative variable:

- Grading of Vitreous Opacity (Altered / Unaltered)

9.6 Extra-cardiac 'red flags' in medical history:

Frequencies (N. %) will be shown for the following qualitative variables:

- Carpal tunnel syndrome (Yes / No). If yes:
 - Have you had surgery (yes / no)
- Lumbar canal stenosis (Yes / No). If yes:
 - Have you had surgery? (Yes / No)
- Gastrointestinal disorders (Yes / No). If yes, a multiple choice table will be shown for:
 - Diarrhea
 - Frequency (< 2/week | 2/week | \geq 3/week)
 - Nausea/vomiting
 - Severe constipation
 - Unintentional weight loss
 - Alternating episodes of diarrhea and constipation
 - Early satiety
- Urological disturbances (Yes / No). If yes, a multiple choice table will be shown for:
 - Urinary tract infections. If yes, descriptive statistics (Mean, SD, Median, Minimum, Maximum, Q1, Q3 and N) of the following quantitative variable will be shown:
 - Number of infections since last visit
 - Urinary retention
 - Urinary incontinence
 - Type (stress / permanent)

- Ophthalmological disturbances (Yes / No). If yes, a multiple choice table will be shown for:
 - Vitreous opacities
 - Glaucoma
 - Conjunctival vessel changes
 - Pupillary changes
- CNS changes (Yes / No). If yes, a multiple choice table will be shown for:
 - Seizures
 - Transient ischemic attack or stroke
 - Cognitive impairment
- Symptoms of autonomic neuropathy (Yes / No). If yes, a multiple choice table will be shown for:
 - Sweating disturbance
 - Sexual dysfunction
 - Grade (Mild / Moderate)
 - Orthostatic hypotension
 - Type (Absent / Dizziness / Syncope)
- Symptoms of peripheral neuropathy:
 - Allodynia/pain (Yes / No). If yes, a multiple choice table will be shown for:
 - Upper limbs. If yes:
 - Grade (Mild / Moderate / Severe)
 - Lower limbs. If yes:
 - Grade (Mild / Moderate / Severe)

- Loss of sensitivity to temperature. If yes, a multiple choice table will be shown for:
 - Upper limbs. If yes:
 - Grade (Mild / Moderate / Severe)
 - Lower limbs. If yes:
 - Grade (Mild / Moderate / Severe)
- Paresthesia / numbness / sensory loss. If yes, a multiple choice table will be shown for:
 - Upper limbs. If yes:
 - Grade (Mild / Moderate / Severe)
 - Lower limbs. If yes:
 - Grade (Mild / Moderate / Severe)
- Muscle weakness (Yes / No). If yes, a multiple choice table will be shown for:
 - Upper limbs. If yes:
 - Grade (Mild / Moderate / Severe)
 - Lower limbs. If yes:
 - Grade (Mild / Moderate / Severe)

